#### **Adverse Events by Maximum Relationship**

Treatment-emergent adverse events will also be summarized by maximum relationship of each preferred term to DAA study drug, pegIFN, and RBV, as assessed by the Investigator. If a subject has an adverse event with unknown relationship, then the subject will be counted in the relationship category of "unknown," even if the subject has another occurrence of the same event with a relationship present. The only exception is if the subject has another occurrence of the same adverse event with a relationship assessment of "Probably Related" or "Possibly Related." In this case, the subject will be counted under the "Probably Related" or "Possibly Related" category, respectively.

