6.3 Relationship to Study Drug

The investigator will use the following definitions to assess the relationship of the adverse event to the use of DAA (ABT-450/r or ABT-267), RBV and pegIFN:

| | |
|-----------------------------|--|
| Probably Related | An adverse event has a strong temporal relationship to study drug or recurs on re-challenge and an Other cause of event is unlikely or significantly less likely. |
| Possibly Related | An adverse event has a strong temporal relationship to the study drug and an Other cause of event is equally or less likely compared to the potential relationship to study drug. |
| Probably Not Related | An adverse event has little or no temporal relationship to the study drug and/or a more likely Other cause of event exists. |
| Not Related | An adverse event is due to an underlying or concurrent illness or effect of another drug and is not related to the study drug (e.g., has no temporal relationship to study drug or has a much more likely Other cause of event). |

For causality assessments, events meeting the categories of probably or possibly will be considered "associated." Events that are probably not or not related will be considered "not associated." In addition, when the investigator has not reported a causality or deemed it not assessable, AbbVie will consider the event associated.

[figure not shown]
If an investigator's opinion of possibly, probably not, or not related to study drug is given, an Other cause of event must be provided by the investigator for the serious adverse event.

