#### **Safety Population**

Subjects who receive at least one dose of study drug will be included in the safety population. The safety population will be the same as the ITT population for this study.

Safety, demographic, and baseline characteristics will be analyzed for the safety population. No imputations for missing data will be performed for analyses of safety data.

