### **Adverse Event Overview**

An overview of adverse events will be presented consisting of the number and percentage of subjects experiencing at least one event for each of the following adverse event categories:

- Treatment-emergent adverse events
- Treatment-emergent adverse events possibly or probably related to DAAs
- Treatment-emergent adverse events possibly or probably related to pegIFN
- Treatment-emergent adverse events possibly or probably related to RBV
- Treatment-emergent severe adverse events
- Treatment-emergent serious adverse events
- Treatment-emergent adverse events leading to study drug (all study drugs) discontinuation
- Treatment-emergent adverse events leading to interruption of study drug (all study drugs)
- Treatment-emergent adverse events leading to RBV dose modifications
- Treatment-emergent adverse events leading to pegIFN dose modifications
- Treatment-emergent adverse events leading to death

- Deaths

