### **Adverse Event by SOC and PT**

For each of the following events, the number and percentage of subjects experiencing treatment-emergent events will be tabulated by SOC and preferred term (PT):

- Treatment-emergent adverse events
- Treatment-emergent adverse events possibly or probably related to DAAs
- Treatment-emergent adverse events possibly or probably related to pegIFN
- Treatment-emergent adverse events possibly or probably related to RBV
- Severe treatment-emergent adverse events

Subjects reporting more than one adverse event for a given PT will be counted only once for that term (most related incident for the relationship tables and most severe incident for the severity tables). Subjects reporting more than one type of adverse event within a SOC will be counted only once for that SOC. Subjects reporting more than one type of adverse event will be counted only once in the overall total.

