### **Adverse Events by PT**

The number and percentage of subjects experiencing treatment-emergent adverse events will be tabulated according to preferred term and sorted by overall frequency. A similar summary will be provided for treatment-emergent adverse events possibly or probably related to DAAs.

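### An adverse event with missing causality is associated under protocol 6.3 but goes to an unknown category under SAP 11.2.1, and by inference is left out of the SAP's drug-related counts

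*SAP*

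**What the plan says.** Protocol 6.3 has the investigator rate each event's relationship to the DAAs, RBV and pegIFN on four levels, none of which is unknown. It then groups them: "events meeting the categories of probably or possibly will be considered" associated, and the two lower levels are not associated. For the gap it adds that "when the investigator has not reported a causality or deemed it not assessable, AbbVie will consider the event associated".

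SAP 11.2.1, under Adverse Events by Maximum Relationship, creates a fifth level: "If a subject has an adverse event with unknown relationship, then the subject will be counted in the relationship category of" unknown, even where another occurrence of that event has a rating. It allows one way out: "The only exception is if the subject has another occurrence of the same adverse event with a relationship assessment of" probably or possibly related.

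The other drug-related summaries in SAP 11.2.1 are defined by the two upper levels alone:

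- **Overview:** "Treatment-emergent adverse events possibly or probably related to DAAs", with matching lines for pegIFN and RBV.
- **By SOC and PT:** the same three lines, for example "Treatment-emergent adverse events possibly or probably related to pegIFN".
- **By PT:** "A similar summary will be provided for treatment-emergent adverse events possibly or probably related to DAAs".
- **By maximum severity:** the same DAA-related repeat as in the PT table.

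SAP 5.1 (Safety Population) adds: "No imputations for missing data will be performed for analyses of safety data". Protocol 8.0 also limits imputation to the HCV RNA endpoints.

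**The concern.** Associated in protocol 6.3 and drug-related in the SAP tables rest on the same two levels. The protocol places missing causality with those levels. The SAP does not, and its change list in Section 12 is silent on this although it records items as small as a change of terminology.

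Safety is part of the primary objective. Protocol 3.2 says that ABT-450/r and ABT-267 had not previously been dosed together with pegIFN and RBV, so the drug-related tables are a main description of how the combination is tolerated. A convention that can move those rates in one direction only should match the protocol, or be declared and justified before the data show how many events it touches.

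**Working it through.** The plan gives no figure to reproduce. The check is a comparison of texts, followed by simple arithmetic for scale.

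**Step 1: one event, two rules.** Take a treatment-emergent event with no causality recorded for the DAAs, in a subject with no other occurrence of that preferred term.

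| Place | Treatment of the event |
|---|---|
| Protocol 6.3 | Associated, grouped with possibly and probably related |
| SAP 11.2.1, maximum relationship | Unknown (stated) |
| SAP 11.2.1, overview, SOC/PT, PT and maximum-severity related tables | Not possibly or probably related, so not counted (inferred) |
| SAP 5.1 and protocol 8.0 | No imputation of safety data, so nothing moves it into a related level |
| SAP Section 12 | Difference not listed |

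This assumes that the SAP's unknown covers both unreported and non-assessable causality. The SAP does not define the term, but the protocol's four levels leave nothing else for it to mean.

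**Step 2: direction.** For a given drug and table row, let A be the subjects with at least one event rated possibly or probably related, and M the subjects with at least one event of missing causality.

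- Numerator under the SAP: |A|.
- Numerator under protocol 6.3: |A ∪ M| ≥ |A|.

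The gap is the number of subjects in M but not in A. It is never negative, and it is zero if every such subject already counts through another related event in that row. In the maximum-severity table the inequality holds for the total on each preferred term. Within that total, a subject with a mild related occurrence and a severe occurrence of missing causality would be shown as mild rather than severe.

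**Step 3: where it can show.** In the overview, a subject is lost only if no other event of any kind is related to that drug. In a preferred-term row, a subject is lost if no other occurrence of that term is related. Individual preferred-term rows are therefore easier to move than the overview lines.

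**Step 4: size.** The protocol synopsis gives up to 35 subjects. Assume N = 35 treated and let k be the number of subjects in M but not in A. The change is k/35:

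- k = 0: 0 points
- k = 1: 1/35 = 2.9 points
- k = 2: 2/35 = 5.7 points
- k = 3: 3/35 = 8.6 points

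With fewer treated, the step per subject is larger (100/N points). The documents give no value for k, so these are illustrations and not a forecast.

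**The case against.** The strongest defence is that the SAP follows the protocol's own statistical section. Protocol 8.0 bars imputation of safety data, SAP 5.1 repeats it, and protocol 8.1.6.1 describes the relationship tabulation without mentioning missing causality. That stands in part: the protocol pulls two ways, and a reader who inferred a plain breach of the protocol would go too far. But 6.3 is the specific rule for exactly this case, and it classifies an event rather than estimating a value. The two sections need to be reconciled in writing.

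Second, the assessor differs. The maximum-relationship table reports the investigator's assessment, whereas 6.3 says how the sponsor will regard the event. That is a good reason to keep an unknown row in that table. It does not settle the other tables, whose descriptions carry no such limit. Nor do the documents confine 6.3 to safety reporting, which has its own Section 6.5. Protocol 6.7 lets either the investigator or the sponsor judge a toxicity to be drug-related.

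Third, the unknown row is visible, all treatment-emergent events are tabulated regardless of causality, and all SAEs are listed. True, but the row shows missing causality by preferred term only. The overview totals cannot be corrected from it, and SAP 11.2.3 plans no listing of events with missing causality.

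Three stronger readings are tempting, and the documents do not support them:

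- **That the SAP expressly removes these events from every drug-related count.** The unknown rule is written for one table only. Exclusion elsewhere is inferred from the table definitions and the no-imputation statement.
- **That the SAP contradicts itself** because it assumes events with incomplete onset dates to be treatment-emergent. That rule decides whether an event falls in the analysis period. The closer comparators, missing severity and missing seriousness, also go to unknown, so the SAP is consistent here.
- **That a particular number of subjects will be affected.** Three relationship assessments per event do not show that any will be left blank.

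**Conclusion.** The point holds as a mismatch between the protocol's specific causality rule and the SAP's convention. It rests on stated text for the maximum-relationship table and on inference for the other drug-related tables. The consequence is one-sided: counts of subjects with drug-related events can only equal or fall below those under protocol 6.3.

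The size is unknown and may be zero. It is 2.9 points per subject if 35 are treated, and only for a subject with no other qualifying event in that row. A reader might infer that the safety conclusion is at risk. The documents do not support that: the study has one arm, no statistical comparisons are planned, and no decision threshold is set on drug-related rates. It should be corrected because safety is part of the primary objective and the correction is cheap.

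**What to change.** In SAP 11.2.1, add a sentence that missing or non-assessable causality is counted as related in the overview, SOC/PT, PT and maximum-severity drug-related tables, following protocol 6.3 and applied separately for the DAAs, pegIFN and RBV. Footnote each table with the number of events and subjects so assigned. State that this is the protocol's classification rule and an exception to the no-imputation statements in SAP 5.1 and protocol 8.0.

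The maximum-relationship table may keep its unknown row, since it reports the investigator's assessment. Section 12 should note that row as an addition to the protocol's four levels.

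If the sponsor prefers to leave missing causality out of the drug-related tables, the minimum is to list and justify the departure in Section 12 and to show the drug-related rates both ways.

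The cost is one SAP sentence, one derivation line and a footnote. The drawback is that drug-related rates may be slightly higher.

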#### **11.2.2 SAEs (Including Deaths) and Adverse Events Leading to Study Drug Discontinuation**

The number and percent of subjects experiencing treatment-emergent SAEs (including deaths), treatment-emergent adverse events leading to discontinuation of study drug (all study drugs), treatment-emergent adverse events leading to interruption of study drug (all study drugs), treatment-emergent adverse events leading to RBV dose modifications, treatment-emergent adverse events leading to pegIFN dose modifications, and treatment-emergent adverse events leading to death will be tabulated according to the primary SOC and PT.

In addition, the number and percentage of subjects with adverse events leading to RBV dose modifications and adverse events leading to pegIFN dose modifications will be tabulated according to the primary SOC and PT, using adverse events with an onset date greater than 30 days post-DAA dosing through 30 days after the last dose of

pegIFN/RBV. For these summaries, only subjects with the maximum of (last RBV dose date, last pegIFN dose date + 7) greater than DAA Study Drug End Day 1 (e.g., last DAA dose date + 1) will be included.

### **11.2.3 Listings of Adverse Events**

The following listings will be provided.

- Listing of subject numbers associated with treatment-emergent adverse events grouped by the primary MedDRA SOC and PT.
- Listing of all treatment-emergent serious adverse events.
- Listing of all treatment-emergent adverse events leading to death.
- Listing of treatment-emergent adverse events leading to discontinuation of study drug (all study drugs).
- Listing of treatment-emergent adverse events leading to interruption of study drug (all study drugs).
- Listing of treatment-emergent adverse events leading to RBV dose modifications.
- Listing of treatment-emergent adverse events leading to pegIFN dose modifications.
- Listing of All Serious Adverse Events (from the Time the Subject Signed the Study Specific Informed Consent Through the End of the Study).

### **11.3 Analysis of Laboratory Data**

Data collected from the local laboratory as a result of additional testing due to an SAE will be used in analyses in addition to the data collected from the central laboratory.

#### **11.3.1 Variables and Criteria Defining Abnormality**

Hematology variables include: hematocrit, hemoglobin, platelet count, red blood cell (RBC) count, white blood cell (WBC) count, platelet count, neutrophils, bands (if detected), lymphocytes, monocytes, basophils (if detected), eosinophils (if detected),

absolute neutrophil count (ANC), prothrombin time, international normalized ratio, and activated partial thromboplastin time (aPTT).

Chemistry variables include: albumin, serum glutamic pyruvic transaminase, (SGPT/ALT), serum glutamic oxaloacetic transaminase (SGOT/AST), alkaline phosphatase, bicarbonate, blood urea nitrogen (BUN), calcium, chloride, cholesterol (total), creatinine, calculated creatinine clearance (using Ccroft Gault equation), direct and indirect bilirubin, gamma glutamyl transferase (GGT), glucose, inorganic phosphorus, magnesium, potassium, sodium, total bilirubin, total protein, triglycerides, TSH, free T4 (if measured) and uric acid.

Urinalysis variables include: specific gravity, ketones, pH, protein, blood, glucose, urobilinogen, bilirubin, leukocyte esterase, and microscopic (reflex).

Additional variables include: IP-10 and total insulin. IP-10 is measured at TI Day 1, TI Week 4, TI Week 24/TI D/C, PR Final/PR D/C, PT Week 24, and PT Week 48/PT D/C. Total insulin is measured at TI Day 1.

The criteria for Potentially Clinically Significant Laboratory Findings are described in [Table 5](#) and [Table 6](#).

**Table 5. Criteria for Potentially Clinically Significant Hematology Values**

Test/Units	Very Low (VL)	Very High (VH)
Hemoglobin		
(mmol/L)	< 4.9	
(g/dL)	< 8.0	
(g/L)	< 80	
Platelet Count		
(cells/mm  )	< 50,000	
(cells/L)	< 50 × 10 	
WBC Count		
(cells/mm  )	< 2,000	> 20,000
(cells/L)	< 2.0 × 10 	> 20 × 10 
ANC		
(cells/mm  )	< 1,000	
(cells/L)	< 1 × 10 	
Lymphocyte Count		
(cells/mm  )	< 500	
(cells/L)	< 0.5 × 10 	
Eosinophil Count		
(cells/mm  )		> 5,000
(cells/L)		> 5 × 10 
aPTT		> 2 × ULN
International Normalized Ratio		> 2 × ULN

**Table 6. Criteria for Potentially Clinically Significant Chemistry Values**

Test/Units	Very Low (VL)	Very High (VH)
ALT/SGPT		$> 5 \times \text{ULN}$ and $\geq 2 \times \text{baseline}$
AST/SGOT		$> 5 \times \text{ULN}$ and $\geq 2 \times \text{baseline}$
Alkaline Phosphatase		$> 1.5 \times \text{ULN}$
Total Bilirubin (mg/dL)		$\geq 2.0 \times \text{ULN}$
Creatinine		
(mcmol/L)		$\geq 132.605$
(mg/dL)		$\geq 1.5$
Creatinine Clearance (mL/min)	$< 50$	
BUN		$> 5 \times \text{ULN}$
Uric Acid		
(mcmol/L)		$> 713.817$
(mg/dL)		$> 12.0$
Phosphate		
(mmol/L)	$< 0.6$	
(mg/dL)	$< 2.0$	
Calcium, Serum		
(mmol/L)	$< 1.75$	$> 3.1$
(mg/dL)	$< 7.0$	$> 12.5$
Calcium, Ionized (mmol/L)	$< 0.9$	$> 1.6$
Sodium (mmol/L)	$< 130$	$> 155$
Potassium (mmol/L)	$< 3.0$	$> 6.0$
Magnesium		
(mmol/L)	$< 0.4$	$> 1.23$
(mg/dL)	$< 0.9$	$> 3.0$
Glucose		
(mmol/L)	$< 2.2$	$> 13.9$
(mg/dL)	$< 40$	$> 250$
Albumin		
(g/L)	$< 20$	
(g/dL)	$< 2$	

**Table 6. Criteria for Potentially Clinically Significant Chemistry Values (Continued)**

Test/Units	Very Low (VL)	Very High (VH)
Protein		
(g/L)	< 50	
(g/dL)	< 5.0	
Cholesterol		
(mmol/L)		> 10.34
(mg/dL)		> 400
Triglycerides		
(mmol/L)		> 5.7
(mg/dL)		> 500

### 11.3.2 Statistical Methods

Mean changes from baseline to each post-baseline visit, including applicable post-treatment visits, will be summarized for each protocol-specified laboratory parameter, including IP-10, with the baseline mean, visit mean, change from baseline mean, standard deviation, and median.

Laboratory data values, excluding IP-10, will be categorized as low, normal, or high based on normal ranges of the laboratory used in this study. Shift tables from baseline to minimum value (related to the normal range), maximum value (related to the normal range) and final values during DAA treatment (DAA Study Drug End Day  $\leq 2$ ) will be created. The shift tables cross tabulate the frequency of subjects with baseline values below/within/above the normal range versus minimum/maximum/final values below/within/above the normal range. The shift tables will also cross tabulate the frequency and percentage of subjects with baseline values below/within the normal range versus minimum/maximum/final values below/within/above the normal range. The shift tables will also cross tabulate the frequency and percentage of subjects with baseline values within/above the normal range versus minimum/maximum/final values below/within/above the normal range.

Frequencies and percentages of subjects with post-baseline chemistry and hematology values during DAA treatment (DAA Study Drug End Day  $\leq$  2) meeting criteria for Potentially Clinically Significant (PCS) Laboratory Values (Table 5 and Table 6) will be summarized. A post-baseline value must be more extreme than the baseline value to be considered as a PCS finding. Listings will be provided that presents all of the subjects and values meeting the PCS criteria (at any time during the study).

For the liver function tests of ALT and AST, the frequency and percentage of subjects with a maximum CTCAE Grade of 1, 2, 3, or 4 (see definitions in Table 8) at any post-nadir visit (regardless of the baseline value) through the end of DAA treatment (DAA Study Drug End Day  $\leq$  2) will be summarized. For hemoglobin, creatinine clearance, alkaline phosphatase, and total bilirubin, the frequency and percentage of subjects with a maximum CTCAE Grade of 1, 2, 3, or 4 (see definitions in Table 7) at any post-baseline visit (regardless of the baseline value) through the end of DAA treatment (DAA Study Drug End Day  $\leq$  2) will be summarized. The summaries will include rows for the number and percentage of subjects with at least Grade 2 and at least Grade 3 laboratory abnormalities. Accompanying listings of all ALT, AST, total, indirect and direct bilirubin, and alkaline phosphatase (as available) will be created for any subject who had at least a Grade 3 ALT, AST, alkaline phosphatase, or total bilirubin. A similar listing will be provided for hemoglobin that includes all hemoglobin, total neutrophils, platelet count, and WBC values and for creatinine clearance that includes creatinine clearance, eGFR and creatinine values.

**Table 7. Definitions of CTCAE Grades 1, 2, 3, and 4 for Liver Function Tests and Hematology**

Test	Grade 1	Grade 2	Grade 3	Grade 4
ALT/SGPT	> ULN – 3 × ULN	> 3 – 5 × ULN	> 5 – 20 × ULN	> 20 × ULN
AST/SGOT	> ULN – 3 × ULN	> 3 – 5 × ULN	> 5 – 20 × ULN	> 20 × ULN
Alkaline Phosphatase	> ULN – 2.5 × ULN	> 2.5 – 5 × ULN	> 5 – 20 × ULN	> 20 × ULN
Total Bilirubin	> ULN – 1.5 × ULN	> 1.5 – 3 × ULN	> 3 – 10 × ULN	> 10 × ULN
Hemoglobin Decreased	< LLN – 100 g/L	< 100 – 80 g/L	< 80 – 65 g/L	< 65 g/L
Creatinine clearance (Cockcroft Gault calculation)	< LLN – 60 mL/min	< 59 – 30 mL/min	< 29 – 15 mL/min	< 15 mL/min

The number and percentage of subjects meeting the following criteria during Substudy 1 [i.e., through the end of DAA treatment (DAA Study Drug End Day ≤ 2)] will be summarized:

- Post baseline and post nadir ALT ≥ 3 × ULN and post baseline total bilirubin value ≥ 2 × ULN;
- Post baseline and post nadir ALT > 5 × ULN (equivalent to Grade 3 or higher) and post baseline total bilirubin value < 2 × ULN.

For subjects meeting the post nadir ALT ≥ 3 × ULN and total bilirubin value ≥ 2 × ULN criterion), a corresponding listing of all ALT, AST, alkaline phosphatase, and total, direct, and indirect bilirubin values will be provided.

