1.2 Synopsis

| | |
|---|--|
| AbbVie Inc. | Protocol Number: M13-101 |
| Name of Study Drug: ABT-450, ritonavir, ABT-267, ribavirin, Pegylated interferon α -2a | Phase of Development: Phase 2b |
| Name of Active Ingredient: ABT-267 ABT-450 ritonavir | Date of Protocol Synopsis: 26 June 2015 |
| Protocol Title: An Open-Label Study to Evaluate the Safety, Antiviral Activity and Pharmacokinetics of Direct-Acting Antiviral Agent (DAA) Treatment in Combination with Peginterferon α -2a and Ribavirin (pegIFN/RBV) in Chronic Hepatitis C Virus (HCV) Infected Subjects Who Have Experienced Virologic Failure in a Previous AbbVie or Abbott DAA Combination Study | |
| Objectives: The primary objective of this study is to evaluate the safety and antiviral efficacy, defined as the percentage of subjects with sustained virologic response 12 weeks post-dosing (SVR ₁₂ ; HCV RNA < LLOQ 12 weeks after the last dose of study drug). The secondary objectives of this study are to evaluate the percentage of subjects with sustained virologic response 24 weeks post-dosing (SVR ₂₄ ; HCV RNA < LLOQ 24 weeks after the last dose of study drug) and the percentage of subjects with extended rapid virologic response (eRVR) (HCV RNA < LLOQ at TI Weeks 4 through 12). | |
| Investigators: Multicenter | |
| Study Sites: Up to 150 sites who participated in a previous AbbVie/Abbott DAA combination study. | |
| Study Population: Subjects who have experienced virologic failure in a previous AbbVie/Abbott DAA combination study. | |
| Number of Subjects to be Enrolled: Up to 35. The enrollment number of this study depends on the treatment failure rate of subjects in previous AbbVie/Abbott DAA combination studies, therefore there will be no lower or upper limit of enrollment. | |

Methodology:

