8. Discontinuation of antiviral therapy due to intolerance or a DAA- or RBV-associated adverse event in the previous AbbVie/Abbott DAA combination study (excluding intolerance or AEs associated with telaprevir).
9. Beck's Depression Inventory-II (BDI-II) score of > 21 at Screening. Subjects with BDI-II score > 21 will not be allowed to rescreen.
10. Clinically significant abnormal ECG, ECG with QT interval corrected for heart rate using Fridericia's correction formula (QTcF) > 470 msec at Screening or TI Day 1 visits.

11. Screening laboratory analyses show any of the following abnormal laboratory results:
- Alanine aminotransferase (ALT) $> 7 \times$ upper limit of normal (ULN);
 - Aspartate aminotransferase (AST) $> 7 \times$ ULN;
 - Calculated creatinine clearance (using Cockcroft-Gault method) < 60 mL/min;
 - Albumin $< LLN$;
 - International normalized ratio (INR) > 1.7 ; (Subjects with a known inherited blood disorder and INR > 1.7 may be enrolled with permission of the AbbVie Study Designated Physician.)
 - Hemoglobin $< LLN$;
 - Platelets $< 90,000$ cells per mm^3 ;
 - Absolute neutrophil count $< 1,500$ cells/ μL (< 1200 cells/ μL for subjects of black/African descent);
 - Indirect bilirubin $> 1.5 \times$ ULN and direct bilirubin $> ULN$;
 - Thyroid stimulating hormone (TSH) values outside the normal range.
12. The use of colony stimulating factors, such as granulocyte colony stimulating factor (GCSF) or erythropoietin within 2 months of the Screening Period.
13. Recent (within 6 months prior to study drug administration) history of drug or alcohol abuse that, in the opinion of the investigator, could preclude adherence to the protocol.
14. Clinically significant abnormalities, other than HCV infection, based upon the results of a medical history, physical examination, vital signs, laboratory profile and a 12-lead electrocardiogram (ECG) that make the subject an unsuitable candidate for this study in the opinion of the investigator.
15. Evidence of infection with other HCV genotypes other than genotype 1 at the Screening Visit.

16. Current enrollment in another clinical study or previous enrollment in this study. Concurrent participation in a non-interventional, epidemiologic or registry trials may be permitted with approval by the AbbVie Study Designated Physician.
17. History of solid organ transplantation.

In addition to Exclusion criteria 1 through 18, subjects with compensated cirrhosis must not meet the following criteria:

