6.7.5 Management of Creatinine Clearance Decreases

If calculated creatinine clearance (by Cockcroft-Gault formula) is confirmed to have decreased to < 50 mL/minute, (in a subject with a baseline creatinine clearance ≥ 50 mL/min), or to below 30 mL/minute (in a subject with a baseline creatinine clearance < 50 mL/min), medical evaluation should include a full review of current medications, including those taken on an as needed basis, those which are sold over the counter and any dietary and herbal supplements, and appropriate dose reduction or discontinuation based on impaired renal function should be done (if applicable). Ribavirin dose should be adjusted as in [Table 13](#). Alternative management of RBV dose in the setting of reduced renal function will require approval of the AbbVie Study Designated Physician.

The investigator should also consider whether drug-drug interactions with concomitant medications may have contributed to the decrease in creatinine clearance, and whether discontinuation or substitution of the possible interacting drug might be needed. For example, drug interactions between DAAs and some antihypertensive medications could potentially increase exposures of the antihypertensive, which may lead to reduction in renal function. If anti-hypertensive medications are adjusted, vital signs should be

monitored to ensure appropriate blood pressure control. Refer to Section 5.2.3 for additional information regarding drug-drug interactions.

Table 13. Dosing of RBV in Subjects with Renal Impairment

| CrCl Value | RBV Dose |
|----------------|--|
| 30 – 50 mL/min | Alternating doses, 200 mg and 400 mg every other day |
| < 30 mL/min | 200 mg daily |
| Hemodialysis | 200 mg daily |

If creatinine clearance improves, the site should perform all necessary readjustment of any dose modifications that have been made. If creatinine clearance improves to above the level that triggered the RBV dose reduction, RBV dose may be increased accordingly.

The Investigator should ensure that any concomitant medication changes, RBV dose reductions, and study drug discontinuations, as well as consequent related adverse events are entered into the appropriate eCRFs.

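### SAP Table 7 gives no creatinine-clearance grade to values of 59 to <60 or 29 to <30 mL/min, so the at-least-Grade-2 and at-least-Grade-3 counts can miss subjects

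*SAP*

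**What the plan says.** SAP Section 11.3.2 summarises the maximum grade per subject through the end of DAA treatment for several laboratory tests, creatinine clearance among them, using the limits in Table 7. For creatinine clearance (Cockcroft-Gault), Grades 1 to 4 read "< LLN – 60 mL/min < 59 – 30 mL/min < 29 – 15 mL/min < 15 mL/min".

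The section then states: "The summaries will include rows for the number and percentage of subjects with at least Grade 2 and at least Grade 3 laboratory abnormalities". It provides a listing for subjects with at least a Grade 3 liver test, and a similar listing for creatinine clearance.

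Three other places bear on the point:

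- Protocol Section 5.2.2 excludes subjects at screening with "Calculated creatinine clearance (using Cockcroft-Gault method) < 60 mL/min".
- SAP Table 6 makes creatinine clearance below 50 mL/min a PCS value. Section 11.3.2 counts subjects with such values during DAA treatment and lists all of them at any time in the study.
- Protocol Appendix C grades serum creatinine but has no creatinine-clearance row. SAP Table 7 is therefore the only definition of these grades.

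**The concern.** The limits do not meet. A value of 59.4 is neither at least 60 (Grade 1) nor below 59 (Grade 2). A value of 29.6 is neither at least 30 (Grade 2) nor below 29 (Grade 3). Creatinine clearance is a calculated, continuous quantity, and the SAP gives no rounding rule for it, so such values can occur.

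The position of the first gap makes it more than a curiosity. Screening requires at least 60 mL/min, so a small fall from an entry value near 60 lands directly in the 59 to <60 band. A subject whose worst value lies there should be counted in the at-least-Grade-2 row if the grades are meant to be contiguous, but under the printed rule is not. The second gap has the same effect on the at-least-Grade-3 row. What is at stake is the accuracy of the renal lines in the graded laboratory summary.

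**Working it through.** **Inputs**

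- Grade limits from SAP Table 7, read as the hemoglobin row of that table must be read (strict upper limit, inclusive lower limit): Grade 1 is [60, LLN), Grade 2 is [30, 59), Grade 3 is [15, 29), Grade 4 is below 15.
- LLN is not given. 90 mL/min is assumed for the examples; the result needs only LLN > 60.
- N = 35, from Protocol Section 1.2: "Number of Subjects to be Enrolled: Up to 35".

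**Step 1: which values have no grade.** The union of the four intervals omits [59, 60) and [29, 30) and nothing else below LLN. In steps of 0.1, the ungraded values are 29.0 to 29.9 and 59.0 to 59.9. On whole numbers they are 29 and 59, so rounding does not close the gaps while the sign is strictly less than. The hemoglobin row (below LLN to 100, below 100 to 80, below 80 to 65, below 65 g/L), treated the same way, leaves no gap.

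**Step 2: does sensible programming rescue it?** A program might test the upper limits in order (<15, <29, <59, <LLN). Then 59 to <60 becomes Grade 1 and 29 to <30 becomes Grade 2. Every value has a grade, but these still miss the at-least-Grade-2 and at-least-Grade-3 rows respectively.

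Maximum grade for three illustrative subjects:

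| On-DAA values (mL/min) | As written | Ordered cut-offs | Contiguous limits |
|---|---|---|---|
| 75, 59.5 | 1 | 1 | 2 |
| 75, 29.5 | 1 | 2 | 3 |
| 75, 45, 29.5 | 2 | 2 | 3 |

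Only a subject whose lowest on-DAA value lies in a gap is affected. One with a lowest value of 29 to <30 stays in at least Grade 2 if another visit is 30 to <59; without such a visit, the literal reading loses that subject from both rows.

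**Step 3: size.** The documents give no distribution, so assume the lowest value per subject is normal with SD 20 and mean μ. Expected number in a gap [a, a+1) = 35 × [Φ((a + 1 − μ)/20) − Φ((a − μ)/20)].

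- First gap, μ = 70: 35 × [Φ(−0.50) − Φ(−0.55)] = 35 × (0.3085 − 0.2912) = 0.61.
- First gap, μ = 85: 35 × [Φ(−1.25) − Φ(−1.30)] = 35 × (0.1056 − 0.0968) = 0.31.
- Second gap, μ = 70: 35 × [Φ(−2.00) − Φ(−2.05)] = 35 × (0.02275 − 0.02018) = 0.09.
- Second gap, μ = 85: 35 × [Φ(−2.75) − Φ(−2.80)] = 35 × (0.00298 − 0.00256) = 0.015.

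With μ of 90 to 100 the first gap holds 0.22 to 0.09 subjects and the second 0.007 to 0.001. Each affected subject moves a row by 1/35 = 2.9 percentage points.

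**Step 4: what other outputs recover.** The PCS criterion (<50 mL/min) captures 29 to <30 in both its count and its listing. It does not capture 59 to <60. The shift tables may show such a value as below the normal range, but they do not grade it.

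**The case against.** The case for leaving this alone concerns consequence, since the limits plainly do not meet. Three stronger readings are tempting, and the documents do not support them.

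- *A reader might infer that a lone Grade 3 renal case could vanish from the report.* It could be missing from the at-least-Grade-3 row, but a value of 29 to <30 is below 50 mL/min, so the PCS count and listing still show the subject. The assumed model also puts fewer than 0.1 subjects there.
- *A reader might infer that both gaps remove subjects from the creatinine-clearance listing.* On the natural reading that listing follows the at-least-Grade-3 trigger of the liver listing. A subject with a lowest value of 59 to <60 would be Grade 2 under contiguous limits and would not be listed either way. Only the second gap can matter.
- *A reader might infer that ribavirin dosing is affected, because the second gap sits just under a dosing boundary in Protocol Table 13* ("< 30 mL/min | 200 mg daily"). Protocol Section 6.7.5 acts on creatinine clearance directly, not on SAP grades.

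Two further objections deserve an answer. First, Table 7 is titled as CTCAE definitions, and the cited source cannot be consulted here, so one cannot say whether the number or the sign was mistyped. That stands, but it does not make the printed row usable. Changing the sign to at most 59 and at most 29 would work only with a whole-number rounding rule, which the SAP lacks. Second, this is one descriptive row in a single-arm study with no statistical comparisons. That also stands, and it limits the weight of the point without removing it.

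**Conclusion.** The point holds as a drafting error that produces a wrong count under the stated rule. Values of 59 to <60 and 29 to <30 mL/min have no creatinine-clearance grade, and neither rounding to whole numbers nor ordered cut-offs puts them in the rows where contiguous limits would.

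The first gap is the one that matters in practice: it adjoins the entry limit, and no PCS summary recovers the subject. The second gap is rarely hit and is backed up by the PCS outputs.

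The expected effect is below one subject throughout the range examined. The probability model behind that is an assumption, and the mean and SD have no source in the documents; the existence of the gaps does not depend on it. Efficacy, the analysis populations and patient management are untouched.

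**What to change.** In SAP Table 7, change the creatinine-clearance entries to Grade 2: < 60 – 30 mL/min and Grade 3: < 30 – 15 mL/min, leaving Grades 1 and 4 as they are, and set the grading program to the same limits. The row then follows the pattern of the others: 59 to <60 becomes Grade 2, 29 to <30 becomes Grade 3, and no value is ungraded.

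The cost is two table cells and the matching program lines. No new data are needed and no clinical rule changes. If the sponsor prefers to keep 59 and 29 for consistency with a source scale, the SAP should instead make those limits inclusive and state that creatinine clearance is rounded to whole numbers before grading.
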